4. SRA+HC+GRC

Random assignments will be generated using a standard random number generator with uniform distribution to the four groups by the Clinical Genomics Study Unit (CGSU) data manager. The research staff (CRC at site) will use this randomization schema to inform participants of their group assignment.

Follow up visits:

6-week and 3-month – At 6 weeks and 3 months after the baseline visit, participants will be asked to complete selected surveys online (Table 1). The 6 week survey must be completed after the counseling visit and before Health Coaching begins.

6-month – Six months from the baseline visit, participants will return to the clinic to have weight, BP and waist circumference measured (same procedures as baseline visit). Medications will be reviewed and AE's assessed.

Female subjects will be asked if they are currently pregnant and this will be documented.

They will also complete the required surveys as listed, either before their scheduled visit or during their visit at the clinic.

12-month- Twelve months from the baseline visit, participants will return to the clinic for a final visit to have weight, BP and waist circumference measured (same procedures as baseline visit). Medications will be reviewed and AE's assessed.

Lab values from the EMR will be documented for fasting glucose, TC, HDL, LDL, TRIG CRC will check in EMR prior to each subject's 12-month visit. If lab values as stated above are not available from the last 6 months of study participation , then a lipid panel (TC, HDL, LDL, TRIG) and either a FBG or HbA1c will be ordered. Female subjects will be asked if they are currently pregnant and this will be documented.

They will also complete the required surveys as listed, either before their scheduled visit or during their visit at the clinic.

Window of ±one week were allowed for all follow up visits. In order to maximize power and considering

Genetic Risk Testing and Health Coaching for CHD and T2D

Duke IRB# Pro00039569 NCT01884545

recent findings on the stability of metabolic clinical markers absent behavior change, statistical analyses will employ extended inclusion windows for study time-points. Statistical analyses will include: +/-3 weeks for the 6 week survey, +/-7 weeks for the 3 month survey, and +/-11 weeks for the 12 month survey.

Table 1.

STUDY VISITS	GROUP 1	GROUP 2	GROUP 3	GROUP 4

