	Risk Assessment Only	Risk Assessment +Health Coaching	Risk Assessment +Genetic Test	Risk Assessment +Health Coaching +Genetic Test
CONSENT**/ BASELINE VISIT	Consent Survey Height, Weight, Waist, BP	Consent Survey Height, Weight, Waist, BP	Consent Survey Height, Weight, Waist, BP Blood Draw	Consent Survey Height, Weight, Waist, BP Blood Draw
RISK ASSESSMENT VISIT	Risk Assessment	Risk Assessment	Risk Assessment + Genetic Result	Risk Assessment + Genetic Result
6 WEEK SURVEY	On-line survey	On-line survey	On-line survey	On-line survey
3 MONTH SURVEY	On-line survey	On-line survey	On-line survey	On-line survey
6 MONTH VISIT	Survey Weight, Waist, BP Meds, Assess AE	Survey Weight, Waist, BP Meds, Assess AE	Survey Weight, Waist, BP Meds, Assess AE	Survey Weight, Waist, BP Meds, Assess AE
12 MONTH VISIT	Survey Weight, Waist, BP Meds, Assess AE, Labs	Survey Weight, Waist, BP Meds, Assess AE, Labs	Survey Weight, Waist, BP Meds, Assess AE, Labs	Survey Weight, Waist, BP Meds, Assess AE, Labs

**Consent may be obtained at a separate visit if HbA1c and/or lipid panel labs need to be performed for eligibility confirmation. If done separately Baseline visit should occur within 4 weeks of consent.

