Additional biweekly calls. HC calls then follow the general template of the coaching prep form. All HC sessions begin with a brief check-in, reporting on specific action steps from the preceding week(s). Participants are trained to note success first, then to problem-solve and explore solutions for upcoming obstacles. Importantly, they learn from failed problem-solving attempts, which are non-judgmentally framed as “experiments” necessary for true learning. Non-judgmental framing is essential to maintaining rapport and encouraging clients to experiment with solutions without fear of failure. Participants then commit to new action steps toward their goals to be accomplished before the next call, and clarify what resources they will need to accomplish them. Of note, the health coaches will be blinded to the participants’ genetic risk results; however, participants may choose to disclose them to the coaches, mimicking actual utilization of this information (Appendix D.).

Table 2. Study Measures	Baseline	6 wks	3 mos	6 mos	12 mos
Eligibility Screen & Informed Consent	X				
Demographic Questionnaire	X				
Family history of CHD & T2D	X				
Blood collection for genetic testing	X				
Primary Outcomes: Behavioral					
Wheel of Health	X	X		X	
Dietary Intake (NCI Multifactor Screener)	X		X	X	X
Physical Activity (SBAS)/Wellness Programs	X		X	X	X
Smoking Status	X		X	X	X
Medication Adherence (Morisky 4)	X	X		X	X
Primary Outcomes: Clinical					
Height for BMI calculation	X				
Weight	X			X	X
Waist Circumference	X			X	X
Blood pressure	X			X	X
Medications	X			X	X
Lab tests (fasting glucose, total cholesterol, HDL, LDL, triglycerides)	X				X
Fitness Status (Air Force Fitness Score)	X				X
Risk Status (FRS and T2D Risk Score)	X				X
Adverse Events Assessed				X	X
Potential Mediators					
Perceived Risk for CHD & T2D	X	X		X	
Worry, Self-efficacy	X	X		X	
Patient Activation	X	X	X	X	X
Stages of Change	X	X	X	X	
Psychosocial Risk Factors: Depression (BDI), stress level (PSS) social isolation (social support item) Hostility (cook-medley)	X X			X	

6. Adverse Events

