Secondary analyses will examine the mediating effects of perceived CHD/T2D risk, self-efficacy, worry, patient activation and readiness for change on the effects of genetic risk information on diet and physical activity at 6 months post randomization. The analytic strategy will be to determine the extent to which genetic risk treatment effects on diet and physical activity occur subsequent to treatment effects on perceived CHD/T2D risk, self-efficacy, worry, patient activation and readiness for change. For example, one set of analyses will estimate the direct relationship between genetic risk counseling and changes in physical activity at 6 months (independent of evaluation of the effects of treatment on perceived risk). Additionally, the extent to which genetic risk counseling influences perceived risk at 6 weeks and 3 months post randomization, *which in turn affects behavior change at 6 months*, will be assessed. This analysis will be repeated using diet as the dependent variable. Then both will be repeated using self-efficacy, worry, patient activation and readiness for change as mediators. In each analysis, mediation will be estimated via a series of linear regressions. Mediation will be *tested statistically* by examining the empirically generated sampling distribution of the parameters involved in the mediational hypothesis: the effect of treatment on the mediators at 6 weeks and 3 months, the effect of the mediators at 3 months on the dependent variable at 6 months, and the product of these effects. We will use bootstrapped sampling distributions of the parameters involved in each mediational hypothesis. Recent work supports this method rather than the more traditional Sobel tests, especially with smaller samples.

9. Protection of Human Subjects

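### Section 8.2 tests mediation through 3-month scores that Table 2 does not schedule for perceived risk, worry or self-efficacy, so 6 of the 10 mediation models cannot be completed as specified

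*Combined protocol and SAP*

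**What the plan says.** Section 8.2 (Analysis Plan) sets out secondary analyses of whether five measures carry the effect of genetic risk information to diet and physical activity at 6 months. The measures are perceived CHD/T2D risk, self-efficacy, worry, patient activation and readiness for change. The stated strategy is to see whether "genetic risk treatment effects on diet and physical activity occur subsequent to treatment effects on perceived CHD/T2D risk" and the other mediators.

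The worked example is perceived risk. It asks how far "genetic risk counseling influences perceived risk at 6 weeks and 3 months post randomization", and whether that in turn changes behaviour at 6 months. The example is run for physical activity and again for diet. "Then both will be repeated using self-efficacy, worry, patient activation and readiness for change as mediators".

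The bootstrap test covers the treatment-to-mediator effect at 6 weeks and at 3 months, "the effect of the mediators at 3 months on the dependent variable at 6 months", and the product of these.

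Table 2 (section 5.3.2) gives the measurement schedule. The rows "Perceived Risk for CHD & T2D" and "Worry, Self-efficacy" are marked at baseline, 6 weeks and 6 months only. Patient Activation and Stages of Change are also marked at 3 months.

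**The concern.** The mediator-to-outcome path in 8.2 needs a 3-month score for every mediator. Table 2 does not collect one for three of the five. If Table 2 is right, the core of the mediation test is missing for those three, and perceived risk is the mediator the plan chose to illustrate the method.

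The analyst would then have to choose a substitute at analysis, possibly after seeing data. Two post-baseline scores are available. The 6-week score comes before the outcome. The 6-month score is taken at the same visit as the outcome, so it cannot show that behaviour changed after the mediator did, and that ordering is what 8.2 sets out to establish. The plan does not say which to use.

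**Working it through.** The plan states no number of mediation tests, so there is no figure to reproduce. The check is a count of 8.2 against Table 2.

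**Step 1. Schedule for each mediator (Table 2).**

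| Mediator in 8.2 | Baseline | 6 wk | 3 mo | 6 mo | 12 mo |
|---|---|---|---|---|---|
| Perceived CHD/T2D risk | X | X | – | X | – |
| Worry | X | X | – | X | – |
| Self-efficacy | X | X | – | X | – |
| Patient activation | X | X | X | X | X |
| Readiness for change (taken as the Stages of Change row) | X | X | X | X | – |

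Worry and self-efficacy share one row. Diet and physical activity are both marked at baseline, 3, 6 and 12 months, so the outcomes are available.

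The blank cells do not look like a text-extraction fault. The two rows directly below keep their 3-month mark, and other rows keep interior blanks (diet at 6 weeks, medication adherence at 3 months). Only the later psychosocial row looks broken, and it is not used here.

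**Step 2. Number of models.** 5 mediators × 2 outcomes = 10. Without a 3-month score: 3 × 2 = 6. Able to run as specified: 2 × 2 = 4. Without a 6-week score: 0.

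**Step 3. What is lost in each of the 6.** Counting the treatment-to-mediator effect once per time point, 8.2 names four quantities:

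- treatment to 6-week mediator: estimable
- treatment to 3-month mediator: not estimable
- 3-month mediator to 6-month outcome: not estimable
- product: not estimable, because any version contains the previous coefficient

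So 3 of 4 are lost, including the product, which is the mediation test itself. The total effect of treatment on the 6-month outcome remains estimable.

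**Step 4. Sensitivity to how the mediators are read.**

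| Reading | Affected | Share |
|---|---|---|
| Base | 6 of 10 | 60% |
| CHD and T2D perceived risk as two mediators | 4 × 2 = 8 of 6 × 2 = 12 | 67% |
| Perceived risk, worry and self-efficacy all split by disease | 6 × 2 = 12 of 8 × 2 = 16 | 75% |
| Readiness for change is not Stages of Change | 4 × 2 = 8 of 10 | 80% |
| Readiness not Stages of Change, and perceived risk split | 5 × 2 = 10 of 12 | 83% |

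None of these alternatives gives a smaller share than the base reading.

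**Step 5. Does another section settle it?** Section 5.3.1 says the 3-month contact is a selection of online surveys and refers to Table 1. The "3 MONTH SURVEY" row of Table 1 names no instruments. Appendix O (Survey) is listed, but its content is not in the text supplied. Section 2 lists stages of change among the potential mediators, which supports the base reading of readiness for change, but it gives no timing.

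**The case against.** The strongest reply is that only a conflict is shown. The survey form decides what was asked at 3 months, and it could carry all three measures, in which case Table 2 has a clerical omission and 8.2 is sound. That stands. The claim of non-estimability is conditional on Table 2.

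The count also rests on reading choices, since no section gives a number of tests. That is true, but the alternatives in step 4 all raise the share.

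The harm may be modest. These are secondary analyses, only two substitute scores exist, and the stated strategy already argues against the 6-month one. That narrows the analyst's discretion but does not remove it, because nothing in 8.2 names the 6-week score as the mediator in the outcome model.

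The 4.5 versus 3 month contrast is nominal. Section 5.3.1 allows ±3 weeks around the 6-week survey and ±7 weeks around the 3-month survey. Assuming 3 months = 13 weeks and an outcome fixed at 26 weeks, the gaps are 20 ± 3 = 17 to 23 weeks (about 3.9 to 5.3 months) and 13 ± 7 = 6 to 20 weeks (about 1.4 to 4.6 months). The ranges overlap, so the contrast is less sharp in practice than the nominal figures suggest.

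Finally, section 5.3.1 requires the 6-week survey to precede health coaching, so a 6-week mediator cannot reflect any coaching, whereas a 3-month one could. This is a real difference in what is measured. It does less damage here because these analyses concern genetic risk information, whose results are given at the counselling visit, before that survey.

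**Conclusion.** The concern holds. Section 8.2 and Table 2 contradict each other. On the Table 2 schedule, 6 of 10 secondary mediation models lack the 3-month mediator score they require, and in each of these the mediation test itself cannot be computed.

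The count assumes that perceived CHD/T2D risk is one mediator and that readiness for change is the Stages of Change measure. It also assumes that Table 2, not 8.2, describes the 3-month form, which the supplied text cannot confirm.

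The scope is limited. The primary aims, the total effects, the 6-week treatment-to-mediator effects and the four models for patient activation and stages of change are unaffected. It should be corrected before analysis because it reaches a majority of the planned mediation tests and leaves the choice of substitute open.

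**What to change.** First compare 8.2 and Table 2 with the 3-month survey form actually used.

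- If the form carries perceived risk, worry and self-efficacy, correct Table 2 and leave the mediation text in 8.2 unchanged.
- If it does not, add to 8.2 before analysis:

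> For perceived risk, worry and self-efficacy the mediator is the 6-week score. The paths are treatment to 6-week mediator, 6-week mediator to 6-month diet or physical activity, and their product, adjusting for baseline mediator and baseline outcome. The 6-month score will not be used as the mediator.

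Keep the 3-month mediator for patient activation and stages of change. The mediation paragraph names no covariates, so state the baseline adjustment for all ten models to keep them consistent. It matches the baseline-adjusted 6-month regression described earlier in 8.2. Also state that readiness for change means the Stages of Change measure, and whether perceived CHD and T2D risk are one mediator or two.

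If 3-month collection is still open, the three measures could be added to that survey, but only participants who have not yet reached 3 months would supply scores.

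The cost is one check of the form and a text edit. No new data are needed, because Table 2 already schedules baseline and 6-week scores for all five mediators. The drawback of the 6-week version is a nominal mediator-to-outcome gap of 6 − 1.5 = 4.5 months, against 6 − 3 = 3 months for the other four models. Indirect effects would not be directly comparable across mediators, and mediator change after 6 weeks would be missed. The text should say so.

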9.1. Ethical Considerations

This study will be conducted in compliance with the protocol, Good Clinical Practice guidelines established by the International Conference on Harmonization, and the ethical standards set forth in the Declaration of Helsinki 2004 (available at: <http://www.wma.net/e/policy/b3.htm>).

9.2. Institutional Review

Prior to patient accrual, this protocol and the protocol informed consent must be approved in writing by the the DUHS Institutional Review Board (IRB). A signed and dated statement that the protocol and informed consent have been approved by IRB will be kept in the study binder in the Principal Investigator's staff office. The term of study approval will not exceed one year. A progress report will be submitted annually to the IRB and re-approval obtained to continue the study. The IRB will also approve any significant changes to the protocol as well as a change of PI. Records of all study review and approval documents will be kept on file by the PI and/or his staff. Adverse events will be reported to the IRB per established policy. The IRB will receive notification of the completion of the study and final report within 3 months of study completion or termination. The PI will maintain an accurate and complete record of all submissions made to the IRB, including a list of all reports and documents. Initial approval letters from each site's IRB will be obtained and submitted to Duke IRB prior to the initiation of the study. During the study conduct sites IRB continuing review letters will be obtained and submitted to Duke IRB annually.

9.3. Monitoring Plan of Participating Sites

Random-sample data quality and protocol compliance audits will be conducted by a team of assigned CGSU staff. Three monitoring events are suggested as a guideline, depending on the quality and volume of data. The first compliance audit will be initiated after 3-5 subjects are enrolled at a site. The second audit will be conducted at study mid-term (after 50% of enrollment is reached) and the last one at the end prior to the data lock (after enrollment is complete and final data has been entered). Audits by the coordinating center may entail: (1) shipping source documents and research records for selected patients from participating sites to the coordinating center for audit, or (2) on-site auditing of selected patient records at participating sites. Audits carried out during the clinical

and reporting phase of this study will ensure that the study is conducted and data are generated, documented, and reported in compliance with the protocol, GCP, and all applicable laws, rules and regulations. This includes inspection of study-related records by the coordinating center auditor and/or its designee, IRB representatives, health authority representatives or the relevant regulatory authorities at any time.

9.4. Protocol Amendments

During the protocol development and review process, each protocol will be assessed for its level of risk and degree of monitoring required. Prior to starting the study, the protocol will be approved by each institution's Institutional Review Board or Independent Ethics Committee (IEC). Amendments to the protocol may be made only with consent of the lead site and the principal investigator and are subject to IRB approval prior to instituting.

9.5. Informed Consent Process

The PI or designee will fully explain the purpose and potential risks and benefits of the study to the subject prior to enrollment and address any questions posed by the subject. In accordance with federal guidelines, all subjects will sign a statement of informed consent which has been approved by the IRB. The subject will receive a copy of the executed consent document. The signed consent will be retained at the investigative site for each subject. The informed consent document serves as authorization as defined under HIPPA and contains the appropriate statements regarding privacy and confidentiality of protected health information (PHI) as well as information on withdrawal from the study. The PI will report to the IRB any changes in the research protocol and all unanticipated problems involving risks to human subjects and others. No changes will be made in the research activity without IRB approval. The investigator or designee will explain to each subject the nature of the study, its purpose, the procedures involved, the expected duration, the potential risks and benefits, and any discomfort the study may entail. Each subject will be informed that participation in the study is voluntary and that he may withdraw from the study at any time and that withdrawal of consent will not affect his subsequent medical treatment or his relationship with the treating physician.

The informed consent will be given by means of a standard written statement, written in non-technical language. The subject will read and consider the statement before signing and dating it, and should be given a copy of the signed document. No patient will enter the study before his informed consent has been obtained.

9.6. Protection of Privacy

Patients will be informed of the extent to which their confidential health information generated from this study may be used for research purposes. Following this discussion, they will be asked to sign the HIPAA form and informed consent documents. The original signed document will become part of the patient's medical records, and each patient will receive a copy of the signed document. The use and disclosure of protected health information will be limited to the individuals described in the informed consent document.

It is the responsibility of the research staff to ensure that protocol subjects received, understands, and signs the informed consent document before enrolling the patient onto this trial. Personnel must provide a HIPAA form and obtain acknowledgment before the subject participates in this study.

10. Risk/Benefit Assessment

10.1. Risks of Drawing Blood:

Risks associated with drawing blood from the subjects arm include minimal discomfort and/or bruising. Infection, excess bleeding, clotting, or fainting are also possible, although unlikely.

10.2. Potential Risk of emotional reactions to the genetic tests results

Participants may have emotional reactions to learning that they do- or do not— carry a gene change for heart disease or diabetes. Participants who feel distressed will be directed to the site study doctor and he may refer them to a genetic counselor or other provider for further assistance as necessary

10.3. Potential Risk of Loss of Confidentiality

Participant information and data will be de-identified and stored on a secured server (REDCap) by the PI and study staff. Hard copies of data will be stored in a locked file drawer in a locked office. Participants may refuse to answer any questions that cause them to feel uncomfortable.

10.4. Alternative

The alternative for potential participants is not participating in the study.

10.4. Benefits:

If participant is enrolled and continues participation through the SRA visit, he/she will learn about their specific risk for future CHD and T2D based on their Framingham Risk and Diabetes risk score.

10.5. Costs to the Subject – there will be no costs to the participant.

